#### *Hypocalcemia*

Aminobisphosphonates are potent inhibitors of bone turnover, and are thus associated with a risk of hypocalcemia.

The normal compensatory mechanism is an increase in parathyroid hormone, which can trigger renal absorption of calcium and vitamin D3 production in response to a decreased calcium efflux from the skeleton after bisphosphonate therapy (Polyzos et al. 2011).

Subjects with abnormal blood calcium or magnesium concentrations, a history of disorders that impair the compensatory increase in parathyroid hormone, or concomitant use of any drug with known potential to cause hypocalcemia will be excluded from the trial. Retesting of out-of-range values is permitted during the enrollment period. Albumin-corrected serum calcium should be considered when serum albumin is below the normal range (e.g., <3.5 g/dL).

All subjects will be provided with supplemental calcium and vitamin D, starting from Visit 1 and continuing through to the end of the trial. Recommended doses are 500 mg to 1000 mg per day elemental calcium and approximately 1000 IU/day vitamin D. A combination product of calcium and vitamin D may be used. Subjects with vitamin D levels below 30 ng/mL at enrollment should receive higher doses of vitamin D during the enrollment period (e.g., 10 000 IU/day for 10 days) to meet the protocol required vitamin D levels. Vitamin D will be reduced to approximately 1000 IU/day prior to the start of treatment at Visit 2. Repeat laboratory testing for vitamin D is permitted during the enrollment period (up to a maximum of 4 times in 60 days). Investigators should promote compliance by instructing the subject to take the supplements as prescribed and by stating that compliance is important for subject safety.

Vitamin D will be measured and reviewed at each visit. If levels of 25(OH)D fall below 30 ng/mL, supplementation of vitamin D should be increased, as appropriate.

#### **Class effect risks of intravenous aminobisphosphonates that may be associated with neridronic acid**

##### *Renal toxicity*

Based on the available data for neridronic acid, there is no clinical evidence for renal safety concerns to date. Nevertheless, renal toxicity was observed in non-clinical studies of neridronic acid and is regarded as a class effect of intravenous bisphosphonates. In most cases, signs for renal toxicity following administration of other intravenous bisphosphonates were transient and reversible after discontinuation of the drug or dose adjustment. Pronounced renal toxicity is a rare event, more common in long-term use, and there is a contributing role of pre-existing renal disease as well as other factors like other medication associated with renal toxicity and dehydration.

Bisphosphonates are rapidly cleared by the kidneys, leading to a high concentration in kidney tissue during and immediately after the infusion. Dose and infusion time are the main factors related to renal toxicity.

In order to mitigate the risk of renal toxicity, subjects with evidence of moderate to severe renal impairment will be excluded (for details, see exclusion criterion 1). Taking into account that renal

toxicity due to intravenous bisphosphonates is related to the maximum drug concentration achieved and not the area under the curve of drug exposure (Khosla et al. 2012), neridronic acid 400 mg will be administered as 4 infusions of neridronic acid 100 mg administered over 240 minutes at Visit 2, Visit 3, Visit 4, and Visit 5.

Due to the potential for renal toxicity with neridronic acid as with other bisphosphonates, renal safety monitoring will be implemented in this trial together with defined stopping criteria (for details, see Section 9.3.2).

#### *Medication-related osteonecrosis of the jaw*

Osteonecrosis of the jaw (ONJ) is a rare adverse effect of bisphosphonate therapy, most commonly reported for patients with multiple myeloma and osteolytic bone metastases receiving repeated monthly infusions for treatment of skeletal related events and bone pain. Factors that may contribute to risk of ONJ include recent tooth extraction, unhealed or infected extraction sites, dental/periodontal disease, improperly fitting dentures causing injury, and prior radiation of the head or neck.

Invasive dental procedures should be avoided during the trial; however, subjects who require emergency dental surgery during the trial should proceed with appropriate treatment including prophylactic antibiotics and frequent follow-up. Subjects should be encouraged to use good dental hygiene (daily flossing and gentle brushing) throughout the trial.

#### *Osteonecrosis of the external auditory canal*

Osteonecrosis of the external auditory canal has been reported with bisphosphonates, mainly in association with long-term therapy. Possible risk factors for osteonecrosis of the external auditory canal include steroid use and chemotherapy and/or local risk factors such as infection or trauma. The possibility of osteonecrosis of the external auditory canal should be considered in patients receiving bisphosphonates who present with ear symptoms including chronic ear infections and/or local risk factors such as infection or trauma.

#### *Atypical femoral fractures*

Although a causal relationship has not been conclusively established, meta-analysis suggests there is an increased risk of atypical femoral fractures in long-term bisphosphonate users. These fractures have a low prevalence (1.1% of all femoral fractures), and the absolute risk to patients receiving bisphosphonates is low. Subjects should be advised to report any thigh, hip, or groin pain, and any patient who develops these symptoms should be evaluated for the presence of an incomplete femur fracture.

#### *Other effects on bone*

Although the potential for deleterious effects on bone following long-term treatment with bisphosphonates remains controversial to this day, no histomorphometric evidence of osteomalacia was reported at doses up to neridronic acid 250 mg in patients with Paget's disease of bone (McCloskey et al. 1987; Atkins et al. 1987), in contrast to findings following administration of the first generation bisphosphonate, etidronic acid.

Supporting the absence of any important effect on bone health, long-term neridronic acid treatment increased BMD and lowered risk of clinical fracture in children and adults with osteogenesis

imperfecta. These results argue against a deleterious effect on bone mineralization due to neridronic acid.

However, the potential for deleterious effects of bisphosphonates on bone has been suggested in conditions of low bone turnover, such as renal osteodystrophy or other adynamic bone disease, although the benefit/risk profile in these conditions is unclear. In addition to exclusion of subjects with chronic kidney disease stage 4 and 5, subjects with known defects in bone mineralization or adynamic bone disease are excluded from the trial.

Monitoring of changes in serum and urinary calcium may be helpful to predict effects of neridronic acid on bone mineralization, since decreases in these parameters, in the context of a compensatory increase in parathyroid hormone, likely indicate ongoing accretion of calcium into bone (McCloskey et al. 1987).

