### **1.3.2 Exclusion criteria**

1. Evidence of renal impairment (estimated glomerular filtration rate [eGFR]  $<60$  mL/min/1.73 m^2 using the 2009 Chronic Kidney Disease Epidemiology Collaboration [CKD-EPI] creatinine equation [Levey et al. 2009] or a urinary albumin creatinine ratio [ACR]  $>150$  mg/g), based on central safety laboratory data obtained prior to Visit 2, or a history of chronic kidney disease. Note: a single repeat laboratory test is allowed.
2. Serum calcium or magnesium values outside of the central laboratory’s reference range, based on central safety laboratory data obtained prior to Visit 2 (a single repeat laboratory test is allowed); a history of hypocalcemia or a metabolic disorder anticipated to increase risk for hypocalcemia (e.g., hypoparathyroidism); concomitant use of drug(s) with known potential to cause hypocalcemia (e.g., aminoglycosides).
3. Vitamin D deficiency, defined as a 25(OH)D level  $<30$  ng/mL, based on central safety laboratory data obtained prior to Visit 2 (up to 4 repeat laboratory tests are allowed). Subjects with vitamin D deficiency should receive appropriate supplementation during the enrollment period. A vitamin D level of at least 30 ng/mL must be documented prior to allocation to investigational medicinal product (IMP).

- 
4. Corrected QT interval (according to Fridericia's formula; QTcF) >470 ms (average of 3 electrocardiograms [ECGs] obtained at Visit 1); serum potassium outside the central laboratory's reference range at Visit 1; clinically unstable cardiac disease, including: unstable atrial fibrillation, symptomatic bradycardia, unstable congestive heart failure, active myocardial ischemia, or an indwelling pacemaker; evidence of complete left bundle branch block; complete atrioventricular block; history of Long QT Syndrome or a relative with this condition; or any other known risk factor for torsades de pointes.
  5. Subjects receiving medications with a known risk of torsades de pointes within 7 days prior to allocation. Subjects receiving selective serotonin re-uptake inhibitor antidepressants (e.g., citalopram, escitalopram) or tricyclic antidepressants are eligible if the QT interval values do not meet the exclusion criteria, the medication was started at least 1 month prior to allocation, the dose is stable, and the dose is anticipated to remain stable until at least 4 days after the last infusion of IMP.

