  6. Anticipated requirement for treatment with oral or intravenous bisphosphonate for another condition such as osteoporosis during the trial, or administration of denosumab (Prolia®) or other drugs affecting bone turnover or bone metabolism within 6 months prior to Visit 1.
  7. History of any allergic or hypersensitivity reaction to neridronic acid or other bisphosphonate, acetaminophen, or to vitamin D or calcium supplements.
  8. Recent tooth extraction or other invasive dental procedure (within 3 months prior to Visit 1), unhealed or infected extraction site, or significant dental/periodontal disease (e.g., impacted molars, severe tooth decay, foci of infection) that may predispose to need for tooth extraction or other invasive dental procedures during the trial. Subjects with indeterminate, suspicious or unreliable dental history, in the opinion of the investigator, must undergo a dental examination prior to receiving treatment.
  9. Evidence of denture-related gum trauma or improperly fitting dentures causing injury.
  10. Prior radiation therapy of the head or neck (within 1 year of Visit 1).
  11. History of malignancy within 2 years prior to Visit 1, with the exception of basal cell carcinoma.
  12. Use of nerve blocks, ketamine infusions, intravenous immunoglobulin, acupuncture, electromagnetic field treatment, or initiation/implementation of radiofrequency ablation or other sympathectomy procedures, or peripheral nerve stimulation within 6 weeks prior to Visit 2.
  13. Evidence of current alcohol or drug abuse, or history of alcohol or drug abuse within 2 years of Visit 1, based on subject history and physical examination and according to the investigator's judgment.
  14. Any other severe medical condition, including severe depression, or any other severe mood disorder, that in the opinion of the investigator may affect efficacy or safety assessments or may compromise the subject's safety during trial participation.
  15. Women who are pregnant or breastfeeding.
  16. Elevated aspartate aminotransferase or alanine aminotransferase >2-fold upper limit of normal, based on central safety laboratory data obtained at Visit 1, or current evidence of chronic liver disease. Safety laboratory testing may be repeated prior to Visit 2, and subjects will be allowed in the trial if results of 2 consecutive tests,  $\geq 3$  days apart, are  $\leq 2$ -fold upper limit of normal.

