f) Vitamin D and calcium supplements will be dispensed to subjects for use during the trial; subjects who are receiving appropriate doses of these supplements may continue without requirement for additional supplementation.

g) Compliance with inclusion and exclusion criteria must be confirmed before allocation to IMP, including pain score of at least 4 on the NRS.

h) Allocation must be performed using the interactive response technology system.

i) Subjects must be assessed prior to each infusion. This includes assessment for signs and symptoms of ocular inflammation, signs of proteinuria (see footnote p), and signs of dehydration. Subjects must be well hydrated prior to the start of infusions. Central safety laboratory data from the previous visit, in particular eGFR, must be evaluated prior to each infusion.

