### **9.2 Inclusion/exclusion criteria**

The trial population must comply with the inclusion/exclusion criteria given in Section 1.3.

Subjects will only receive IMP if documentation is available showing that they comply with all of these criteria.

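### Protocol Section 8.2 says subjects with known mineralization defects or adynamic bone disease are excluded, but none of the 20 exclusion criteria excludes them

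*Protocol*

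**What the plan says.** Protocol Section 8.2, under the paragraph on other effects on bone, says that harm from bisphosphonates has been suggested where bone turnover is low, giving renal osteodystrophy and other adynamic bone disease as examples, "although the benefit/risk profile in these conditions is unclear". It then states that, over and above the exclusion of chronic kidney disease stages 4 and 5, "subjects with known defects in bone mineralization or adynamic bone disease are excluded from the trial".

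Eligibility is decided elsewhere. Section 9.2 refers to the criteria in Section 1.3 and adds: "Subjects will only receive IMP if documentation is available showing that they comply with all of these criteria". Footnote g to the schedule of events (Section 1.6) repeats the requirement: "Compliance with inclusion and exclusion criteria must be confirmed before allocation to IMP". Section 1.3.2 lists exclusion criteria 1 to 20.

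**The concern.** The protocol claims a safeguard in its benefit/risk section that its eligibility list does not contain. Sites check subjects against Section 1.3, so a subject whom the sponsor says is kept out could be allocated and given up to 400 mg without failing a listed criterion. Section 9.3.1 notes that bisphosphonates are retained in bone for a long time, so stopping the infusions early would not undo an inappropriate exposure.

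There is a smaller consequence for the bone-safety data. Osteomalacia is a collected outcome (Sections 1.2 and 14.1.6.3), read from a single post-treatment biopsy at about Week 26 with no baseline biopsy (Section 12.3.8). The exclusions specific to the biopsy subset in Section 8.2 concern bleeding risk, oral contraceptives and tetracycline allergy, not existing bone disease. A mineralization defect present before treatment could therefore be read as a drug effect.

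**Working it through.** The plan gives no figure to reproduce. The check sets the exclusions asserted in Section 8.2 against the numbered criteria in Section 1.3.2.

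**Step 1. Does any criterion name the conditions?** The list runs from 1 to 20 with no gap in the numbering, so a removed or redacted item does not explain the absence. Criteria naming a bone mineralization defect, osteomalacia or adynamic bone disease: 0 of 20. The list of forbidden medications in Section 1.4.3 covers drugs and procedures, not bone diagnoses.

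**Step 2. Which criteria cover part of the group?**

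| Criterion | What it tests | What it leaves open |
|---|---|---|
| 1 | eGFR <60, urinary ACR >150 mg/g, or history of chronic kidney disease | Non-renal bone disease |
| 2 | Calcium or magnesium out of range; hypocalcemia history or risk | Disease with normal values and no expected hypocalcemia risk |
| 3 | 25(OH)D <30 ng/mL, correctable by supplementation with up to 4 repeat tests | Disease with vitamin D at or above 30 ng/mL |
| 6 | Expected need for a bisphosphonate; denosumab or "other drugs affecting bone turnover or bone metabolism within 6 months prior to Visit 1" | Any diagnosis not treated with such a drug |
| 14 | Other severe conditions "that in the opinion of the investigator may affect efficacy or safety assessments" or compromise the subject's safety | Disease the investigator does not judge severe |

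Partial or discretionary cover: 5 of 20. If criterion 6 is set aside because it concerns drug use and not a diagnosis, the count is 4 of 20. Neither count changes the result of Step 1.

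**Step 3. Can a subject pass?** Take known non-renal disease, eGFR and ACR within limits, calcium and magnesium in range, no anticipated hypocalcemia risk, 25(OH)D of at least 30 ng/mL, no recent or planned bone-active drug, and a condition not judged severe. On the bone disease alone, no criterion is met and the subject is eligible.

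**Step 4. Is this how Section 8.2 normally works?** The whole-trial exclusions it states are:

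- calcium and magnesium disorders, including drugs that cause hypocalcemia: criterion 2;
- renal impairment: criterion 1, which Section 8.2 cites by number;
- pregnancy or lactation: criterion 15;
- known mineralization defect or adynamic bone disease: none.

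Matched: 3 of 4.

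**Step 5. Possible effect on the biopsy result.** About 15 evaluable specimens are planned. If one came from a subject with an existing mineralization defect that met the Section 14.1.6.3 definition, it would add 1/15 = 6.7 percentage points to the observed proportion with osteomalacia. This is conditional on such a subject entering the subset; the documents give no basis for how likely that is.

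**The case against.** The strongest reply is that little is left uncovered. Criterion 1 excludes any history of chronic kidney disease and so should catch renal osteodystrophy, the one specific disease that Section 8.2 gives as an example. Criteria 2 and 3 catch many metabolic cases, and criterion 14 lets an investigator exclude a severe case. Principal investigators sign their agreement to the whole protocol (Section 5.1.1), including the Section 8.2 sentence, and can stop the drug at any point if they see undue risk (Section 9.3.2). The same part of Section 8.2 also reports no histomorphometric osteomalacia at doses up to 250 mg in Paget's disease. Finally, the sentence describes the renal exclusion more narrowly than criterion 1 does, so it may be loosely drafted narrative and not an intended criterion.

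Much of this stands as a limit on size: the remaining group is narrow. It does not remove the contradiction. Section 8.2 presents the bone exclusion as additional to the kidney exclusion, so criterion 1 cannot be its source. Criterion 14 requires severity and depends on opinion, whereas the stated exclusion is categorical for known disease. Signing the protocol does not change the fact that Section 9.2 ties dosing to Section 1.3. The Paget's data come from a different population and a lower dose than 400 mg. Nor is detection assured: routine history beyond CRPS covers 3 years plus whatever earlier history is thought relevant, and treating physicians' records need not be obtained (Section 12.2.3).

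**Conclusion.** The point holds. The protocol states a categorical exclusion that its operative criteria do not deliver: 0 of 20 criteria name the conditions, 5 of 20 give partial or discretionary cover, and this is the only one of the four whole-trial exclusions in Section 8.2 without a numbered criterion. The number of subjects affected cannot be estimated from the documents and is expected to be very small. The primary endpoint analysis is not in question. The conclusion assumes that sites apply Section 1.3 as written and that an investigator does not use criterion 14 to fill the gap. It should be corrected because it concerns patients for whom the protocol itself regards benefit/risk as unclear.

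**What to change.** Add one exclusion criterion to Section 1.3.2: *Known defect in bone mineralization (e.g., osteomalacia) or adynamic bone disease.* If the sponsor does not intend this exclusion, the Section 8.2 sentence must instead be corrected so that it no longer claims it; adding the criterion is preferable because it provides the protection already described.

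The cost is one line in an amendment. Amendments 01, 02 and 03 each added an exclusion criterion (numbers 5, 19 and 20 in the current list), so this is routine. The downside is that a very small number of otherwise eligible subjects would be excluded.

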### **Additional information relevant for the safety profile**

#### *Pregnancy and breastfeeding*

There are no adequate and well-controlled trials of neridronic acid in pregnant or lactating women. Although there are no data to suggest a fetal risk in humans, bisphosphonates do cause fetal harm in animals, and animal data suggest that uptake of bisphosphonates into fetal bone may be greater than into maternal bone. Therefore, neridronic acid should not be administered during pregnancy and lactation and as a result, pregnant or lactating women are excluded from participation in this trial.

Women of child-bearing potential must have a negative urine  $\beta$ -HCG pregnancy test at the Enrollment Visit and prior to each infusion of IMP. Trial subjects must use contraception as defined in inclusion criterion 6.

#### **Risks related to acetaminophen and calcium and vitamin D supplementation**

High doses of acetaminophen may cause hepatotoxicity and can lead to liver failure. Subjects who take acetaminophen for prevention or relief of symptoms of the acute phase reaction during the treatment period will be reminded that the total dose must not exceed 4 g/day and that caution should be exercised since acetaminophen may be present in many over-the-counter drugs, particularly analgesic medications.

Recommended daily doses of calcium and vitamin D are lower than the tolerable upper intake level, at which there is no risk to healthy individuals (Ross et al. 2011; Rosen et al. 2012). Short courses of high doses of vitamin D are anticipated to pose no significant risk to trial participants.

#### **Risks related to bone biopsies**

Bone biopsies are performed as a minor outpatient surgery and are safe and generally well-tolerated (Kann et al. 2006, Hernandez et al. 2008). Risks include bleeding, hematoma, infection, superficial nerve injury, and pain. Most subjects experience soreness over the biopsy area for 4 days to 5 days. Subjects with increased risk of bleeding (e.g., hemostasis disorders, concomitant treatment with antithrombotic drugs) will be excluded from the bone biopsy assessments.

It is unknown whether a bone biopsy could trigger or worsen CRPS in patients. The limited trials in which bone biopsies were performed in patients with CRPS or similar painful conditions have not suggested that this procedure would be likely to cause severe complications or worsening of CRPS, even when performed in a CRPS-affected region. Since biopsies will be performed only in a region

free of CRPS-related signs and symptoms, this is likely to mitigate the risk of worsening of the condition.

Side effects from tetracycline are rare, but may include skin rashes, photosensitivity, nausea and diarrhea. Women of child-bearing potential using oral contraceptives will be excluded due to potential risk that tetracycline may diminish contraceptive efficacy. Subjects with known allergy to tetracyclines will also be excluded.

### **Risks related to bone densitometry and magnetic resonance imaging**

Bone densitometry using DXA is safe and well tolerated; radiation doses are very low (<5 µSv), generally 10-fold lower than a chest x-ray and 20-fold lower than a standard dental x-ray procedure.

Risks of MRI are due to metallic implants or other ferromagnetic foreign bodies that may be displaced and accelerated toward the magnet, causing tissue damage. Tattoos and cosmetics may contain particles of iron oxide or other metals and may cause burns or local irritation during MRI procedures. Claustrophobic reactions can occur. Ionizing radiation is not involved.

The investigator will assess the appropriateness of the subject for inclusion in the imaging subset and discuss the risks with the subject during the consenting process.

